#### 6. **Other Data Security Measures:**

In addition to the details regarding data collection, please review the following questions. This additional information will be utilized to assist in the development of a comprehensive Data Security plan. This would include the systems used to analyze the data, data security contacts and additional requirements.

1. During the analysis phase, do you plan to use computer systems that are not managed by JHSPH or JH? Yes  No   
If yes, please explain: [The team in Pakistan will have the data on their server at HDRF as it is collected. \(See #5 above on page 21-22\)](#)
2. Do you have a designated person on your research team other than the PI who is the technical contact for a Data Security plan? Yes  No   
If yes, please provide a contact name: [[name].](#)
10. Does your sponsor have other specific data security requirements for the study data? Yes   
No   
If possible, please explain:

3. Please add any other information that you believe is relevant to data security.

#### 4. **Certificate of Confidentiality:**

All NIH studies include Certificate of Confidentiality protections with the grant; the consent form must include the C of C language provided in our template. Other funders may obtain C of C protections through NIH. (<https://humansubjects.nih.gov/coc/index>)

Does the study have Certificate of Confidentiality protections?

Yes  No

#### 5. **JHM Clinical Records:**

Will you use clinical data of 500 records or more from Johns Hopkins Hospital and its affiliates?  
 Yes  No

If yes, please complete the JHM Data Security Checklist available on the JHSPH IRB website: [www.jhspph.edu/irb](http://www.jhspph.edu/irb) and upload a copy of the checklist to the “Miscellaneous” section.

## **VII. Risks of the Study:**

- Describe the risks, discomforts, and inconveniences associated with the study and its procedures, including physical, psychological, emotional, social, legal, or economic risks, and the risk of a breach of confidentiality. These risks should be described in the consent documents.

The proposed HMHB intervention is based on tried and tested principles of CBT, which are safe and effective and considered one of the first lines of treatment for anxiety (77)

We do not foresee any potential long-term risks associated with the intervention. Potential immediate risks and discomforts anticipated with the research procedures are given below:

- Pregnant women may find it difficult to talk about
  - stressful experiences in their lives while answering structured questionnaires containing scales (e.g., about CMDs, healthcare utilization, etc.) resulting in distress.
  - experiences of intimate partner violence (IPV) while answering structured questionnaires.
- HMHB non-specialist providers may find working with anxious or depressed individuals distressing.
- Non-specialist providers may divulge information about anxious or depressed women to others, a breach of confidentiality.
- A large number of survey measures could cause respondent burden.
- Blood draw: Risks are minimal but include temporary discomfort, bleeding or bruising and rarely infection and light-headedness/fainting. If light-headedness/fainting occurs the subject will be monitored by a member of the research team and will not be released until the event has resolved.
- Describe the anticipated frequency and severity of the harms associated with the risks identified above; for example, if you are performing “x” test/assessment, or dispensing “y” drug, how often do you expect an “anticipated” adverse reaction to occur in a study participant, and how severe do you expect that reaction to be?

We expect the severity of the discomfort of participation in intervention sessions and questionnaire completion to be no greater than what women experience normally while talking about their feelings in daily life. We also believe that the possibility of breach of confidentiality and stigmatization is very low. All the interviewers and non-specialists piloting the intervention content will be trained on maintaining confidentiality. All of the research staff will be trained to use non-stigmatizing terms/language. Similarly, the intervention content will use non-stigmatizing terms/ language. Adverse events related to the blood draw are expected to be extremely infrequent.

- Describe steps to be taken to minimize risks. Include a description of your efforts to arrange for care or referral for participants who may need it.

**Plan to minimize risk (a):** Study staff members who administer questionnaires to participating women will be trained to be sensitive and to identify any psychological symptoms/distress that participating women may experience while answering the questionnaires. Although we will be using non-specialized providers as HMHB Trainers, staff trained in counseling will be available, who can be called upon if participants are mildly distressed. For more severe distress we will follow hospital protocols for referral/services.

Also, prior to the initiation of the study, all medical staff based at the Department of Obstetrics will be trained/oriented in the WHO Mental Health Gap Action Program (mhGAP) treatment guidelines to address any

referrals from the research team. Apart from the training of medical staff of hospital, referrals will be made to the Institute of Psychiatry (IoP), Rawalpindi, the district tertiary care hospital.

Additionally, to reduce the burden on women participating in the study we will provide the option of taking breaks between questionnaire sections and/or have the option of having the questionnaire administered in two sittings. Participants will be instructed that they may decline to answer or discontinue participation from the study at any time.

**A. Participants may find it difficult to talk about experiences of intimate partner violence (IPV) in their lives while answering structured questionnaires.**

**Plan to minimize risk (B):** We recognize IPV is an issue that is associated with both anxiety and depression. It has high prevalence rates in urban Pakistan (47). All women will be assessed on a IPV screener at the baseline and 3rd trimester visits as well as the 2013 DHS IPV instrument at the six-week postpartum visit. This will allow us to identify any women needing referrals because of IPV. All women participating in the study regardless of study arm will receive information about where they can seek care for IPV (i.e. the Institute of Psychiatry.) This program, like our prior Thinking Healthy Program (THP) that used CBT to reduce depression, includes several components – related to family engagement, education, problem solving, facilitating women to tap into their support networks– that will help address potential IPV. We have also identified potential interventions based on the WHO's Problem Management+ (PM+) (48, 49) for IPV, which are being reviewed in detail before the start of the trial. Women who report IPV will be referred to the Institute of Psychiatry, Rawalpindi Medical College, where they can receive social services and support for IPV.

**B. There may be some women experiencing extreme distress.**

This issue will be addressed in the following way:

**Step 1:** We will exclude depressed cases at the screening stage and refer them to their physician at the hospital (who will have been given mhGAP training). If a woman is suicidal then she will be referred to psychiatric and/or psychological care the hospital. For non-life threatening less extreme distress, but high symptom levels of anxiety or depression, the participant's obstetrician or primary care provider will be alerted to undertake further assessment and to make appropriate referrals.

**Step 2:** For any women who may develop depression during the trial (who were not depressed at baseline/enrollment), we will follow the same procedure for referrals (above). Evaluation of whether depression is developed will be based on identification from the HMHB trainer, a member of the assessment team, or hospital staff (who will have all received MhGAP training in mental health). If they find someone they suspect who is developing depression, they will contact Co-I [name] (a psychologist) and Co-I [name] (a psychiatrist) to further investigate and determine when referrals are necessary. The HMHB trainers will be regularly supervised by [name] (the master trainer) and the assessors will be regularly supervised by [name] (the site psychiatrist).

**E. Large number of survey measures could lead to respondent burden.**

**Plan to minimize risk (F):** We will be mindful of the burden on participants and will streamline the data collection process by training our research staff both to 1) make data collection efficient, and 2) be sensitive to participant fatigue and signs of distress.

In order to prevent as much respondent burden as possible, we will provide participants the option of taking breaks between questionnaire sections and/or having the option to complete the questionnaires in two sittings. Finally, research staff trained in counselling techniques will be available who can be called upon if participants are mildly distressed. For more severe distress we will follow the protocol for referral/services outlined in our human subjects section.

Also, to protect against risks and monitor the trial and activities described, a Trial Steering Committee (TSC) consisting of Drs. [name], [name], [name], [name], [name], [name], [name], [name], the data manager (TBD) and representatives of the NIMH will oversee this study and take necessary steps to further mitigate any potential risks. The TSC will meet before the trial commences to approve the final protocol and on a weekly basis to monitor trial conduct and progress. Meeting minutes will be kept to document ongoing issues, to keep the study on track, and to ensure that steps are taken to address any issues needing attention and that they dealt with appropriately. The TSC will also submit progress reports with updates to the local IRB at the Human Development Research Foundation (HDRF) as well as the Data Safety and Monitoring Board (DSMB).

**F. Blood Draws**

**Plan to minimize Risk F:** The blood will be drawn by a trained professional (physician, nurse, phlebotomist, or trained study team member). In all cases, aseptic technique will be practiced while obtaining the venous blood samples. If lightheadedness or syncope occurs the subject will be monitored by a member of the research team and not released until resolved. If any unforeseen complication occurs, the patient will be examined by a physician and an appropriate course of action as determined individually and as medically warranted. All personnel will undergo training for safe handling and storage of bodily fluids.

## COVID-19 Exposure Contingency Plans

Research team members who are found to be COVID-19 positive or experience unprotected exposure to COVID-19 will be referred to care, sent home or to the appropriate facility for required treatment, and instructed to self-isolate. These team members will not have subsequent interaction with study participants before resolution of their infection, with all research study visits or other in-person activities being transferred to other staff or rescheduled to avoid exposure of participant or other staff. The staff members' equipment and workplace will be sanitized.

COVID-19 positive or exposed research study participants will be referred for appropriate testing and/or treatment and will be interviewed by phone or in person to determine possible contacts among other study participants or study staff and facilitate contact tracing. These participants will not engage in any in-person study activities until resolution of their infection. Study staff who interacted with these participants without appropriate PPE will not carry out further in-person duties until they are tested and/or complete 14 days of isolation.

- Describe the research burden for participants, including time, inconvenience, out of pocket costs, etc.

Participants may feel tired or upset by talking about stressors or concerns that make them anxious. We will allow them to take breaks if they feel the interview is long or that they would like to take a break. We will also offer them counseling, if they indicate the need for it or if we consider that they could benefit from it. We will reimburse women for transportation costs to interviews and intervention group sessions.

- Describe how participant privacy will be protected during data collection if sensitive questions are included in interviews.

All interviews and sessions will be conducted, to the extent possible, in privacy. The assessment team and non-specialist providers will be trained to explain to family members (accompanying the participant) why it is important for the interview/session to be carried out privately, unless the participant requests for family member/s to be present.

## **VIII. Direct Personal and Social Benefits:**

- Describe any potential direct benefits the study offers to participants ("payment" for participation is not a direct personal benefit).

**Individual benefits:** Participation in this study may confer both physical, psychological, and other benefits. First, CBT methods that are indicated for anxiety(50) will be used to address major stressors during pregnancy. These methods have the potential to directly help women and reduce symptoms of anxiety, as well as have beneficial effects on depression (which is highly correlated with anxiety and for which symptoms of anxiety are a risk factor). Women in the intervention and control groups who are identified as having life-threatening mental health conditions (i.e., severe depression or active suicidal ideation) will be referred immediately for psychiatric and/or psychological care. Ultrasound re-imbursement will also be a benefit of the study.

- Describe potential societal benefits likely to derive from the research, including value of knowledge learned.

**Societal Benefits:** The research has the potential to make a major contribution toward addressing prenatal anxiety, which could have downstream benefits to prevent both later anxiety and depression as well as adverse outcomes for children. It will advance our knowledge regarding whether such an intervention can achieve benefits for mothers and their children in these domains. In addition, the analysis of mediators will provide the opportunity to learn about potential mechanisms that could be targeted to enhance the intervention upon scale-up. Evaluation of effect modifiers is important for this research as it allows us to learn in which subgroups of women

the intervention may be more or less effective. The economic evaluation will also inform how available funds can be used most efficiently, providing useful policy-relevant information needed for the potential scale-up of such a program. If successful, the HMHB intervention could provide evidence to inform more effective public health interventions and public policies to promote lifelong maternal mental health and resilience across generations and provide information to inform resource budgeting for such programs.

## **IX. Payment:**

1. Describe the form, amount, and schedule of payment to participants. Reimbursement for travel or other expenses is not “payment,” and if the study will reimburse, explain.

Pregnant women participants may receive approximately equivalent to \$4.00 US dollars as a thank you for their time and to facilitate transportation. They will also receive reimbursement for ultrasound scans during the course of their pregnancies (normally charged by the hospital, which cost ~\$1.00), as indicated by the obstetrician/gynecologist taking care of the participant. We will also give each mother a present in the form of children’s clothes as a token of our appreciation at the conclusion of the study (~\$4.00 USD). For women who have lost a fetus or baby we will give them the equivalent in household items. Women who participate in the biological substudy will also receive a baby gift worth approximately \$10 US.

2. Include the possible total remuneration and any consequences for not completing all phases of the research.

## **X. Study Management:**

### **A. Oversight Plan:**

1. Describe how the study will be managed.

The Trial Steering Committee (TSC) is comprised of key personnel from research team, a NIMH Program Official and a DSMB liaison. The TSC is chaired by the study PI and Site Co-PIs. The PI and Site Co-PIs will be primarily responsible for monitoring the trial. All the named investigators have previously conducted clinical trials of this type. The PI will be in regular contact with the local investigators and staff via trial management structures, as well as additional in-person contact or via email, when required. The trial steering committee will meet between once a week (during enrollment) to once a fortnight (following enrollment until the completion of the trial). Its role is to monitor all aspects of the conduct and progress of the trial and ensure that the protocol is adhered to.

2. What are the qualifications of study personnel managing the project?

4. If the PI will not personally be on-site throughout the data collection process, provide details about PI site visits, the supervision over consent and data collection, and the communication plan between the PI and study team.

The PI will have weekly calls with the team, and local supervision of consent and data collection will be monitored by Drs. [name] and [name] (as described above in #1). The PI will also make at minimum yearly site visits. The leadership team will meet in Baltimore and Liverpool once a year for face-to-face team meeting (including not only Drs. [name], [name], [name], [name] and [name] but also including [name]). Drs. [name] and [name] will participate in the Baltimore based face-to-face meetings.

#### **B. Recordkeeping:**

Describe how you plan to ensure that the study team follows the protocol and properly records and stores study data collection forms, IRB regulatory correspondence, and other study documentation. For assistance, contact [[contact]](mailto:[contact]).

Drs. [name] and [name], as the local-PIs, will be monitoring this regularly. During our weekly calls the PI will inquire and monitor any issues about how these records are being stored and data collected. Furthermore, the PI will check on this during site visits. Other study documentation can be sent to the PI at Hopkins for review. An NIMH appointed Data Safety and Monitoring Board will also be included in our calls and will provide additional advice and guidance as any issues come up. During the formative phase (IRB #7678) representatives from the IRB joined regularly in our monthly research management meetings. They have indicated that they will also attend our meetings during the trial phase.

#### **C. Safety Monitoring:**

1. Describe how participant safety will be monitored as the study progresses, by whom, and how often. Will there be a medical monitor on site? If yes, who will serve in that role?

Throughout the study, the TSC will provide updates on regulatory matters, recruitment, safety issues and works closely with Data Safety and Monitoring Board (DSMB). The TSC will oversee this study and take necessary steps to further mitigate any potential risks. The DSMB will inform the TSC of any signals or concerns regarding the protection of participant safety. The DSMB has decision making authority, and decisions made by the DSMB will not require ratification by the investigators. The TSC will also submit progress reports/updates to the local IRB at HDRF as well as the DSMB.

2. If a Data Safety Monitoring Board (DSMB), or equivalent will be established, describe the following:

- a. The DSMB membership, affiliation and expertise.

[This has been determined by NIMH](#)

- b. The charge or charter to the DSMB.

[TBA](#)

- c. Plans for providing DSMB reports to the IRB.

[TBA](#)

6. Describe plans for interim analysis and stopping rules, if any.

[We have no plans for interim analyses for the effects of the trial or stopping plans.](#)

**D. Reporting Unanticipated Problems/Adverse Events (AEs) to the IRB (all studies must complete this section):**

Describe your plan for reporting to the IRB and (if applicable) to the sponsor. Include your plan for government-mandated reporting of abuse or illegal activity.

- AEs detected by the assessment team will be collected systematically on smart phones/tablets (electronic data collection) during all outcome assessments. These will be uploaded daily to the database and the data manager will complete a daily report (detailing the participant's Trial ID, type of AE and date of the event) and forward this to the [name] (Co-I).
- AEs detected by the non-specialist providers will be first reported to [name] (one of the site PIs) who will complete the AE report on smart phones/tablets. These will be uploaded to the database and the data manager will complete the report (detailing the Trial ID, type and date of the event) and forward it to the study coordinator.
- The data manager will forward the AEs to the nominated independent psychiatrist, [name], MBBS (Department of Obstetrics and Gynecology at HFH) who is not associated with the research study or to an independent physician. [name] will do a home visit or have a telephone call with the respective participant or family member in the case of death to inquire about the details of the event and to suggest mitigation strategies (as outlined above). This assessment will be documented in a detailed narrative report regarding the nature of the AE, its relationship to the intervention, actions taken since then and actions recommended.
- The data manager will mask the participant's identity (by eliminating any identifiable information) and send these detailed narrative reports to [name] (one of the site PIs) who will in turn forward this information to the PI.
- The site PIs will forward this report to the local IRB as well as document it in periodic updates for JHU.

NOTE: The IRB does not require PROMPT reporting of all AEs, only those that are unanticipated, pose risk of harm to participants or others, and are related to the study. Anticipated AEs may be reported with the Progress Report.

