Recruitment / Consent / Randomization: Pregnant women coming for their initial prenatal visit will be screened for eligibility; this includes being “at risk” for anxiety on the anxiety subscale of the Hospital Anxiety and Depression Scale (HADS) or having moderate or high levels of anxiety (i.e. a cutoff of  $\geq$  score of 8). Informed consent will be obtained from eligible women and those agreeing to participate will be individually randomized to either the HMHB intervention or enhanced usual care (the control). A randomization sequence with varying block size (i.e. randomly permuted sizes of 4, 6, 8, and 10) will be generated by an independent researcher who is located off-site (Institute of Psychiatry, Rawalpindi, Pakistan) and is not involved in running of the study. The individual allocations will be provided to the study staff in opaque sequentially-numbered envelopes and utilized sequentially at the time of enrollment of each participant. Each woman randomized into the HMHB group will be assigned to a HMHB non-specialist provider to introduce them to the program.

Intervention Group: Women allocated to this group will receive the HMHB intervention. The content of HMHB will be based on 1) formative research (completed last year), 2) prior cognitive behavior therapy-based approaches to

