Pregnancy conditions: medical status in pregnancy (e.g. pre-eclampsia, gestational diabetes)	X			X	X	X
Adverse event review					AT ALL TIMES	

\*Baseline assessment may be the same day or up to two weeks after screening.

Note: Full descriptions of the assessment tools are given in section 8.2.3.

\*\*Assessments will be somewhat flexible; the 6-week postpartum visit can be done a week early and up to three weeks after the 6 week mark (if scheduling issues preclude collecting data exactly at the desired time)

§This screener will be administered in order to be able to refer women with IPV to counseling, since it is considered an adverse event.

§§Anthropometry will be measured either our team or a healthcare provider at the 6 week postpartum visit.

[figure not shown]
2. Describe the number and type of study visits and/or contacts between the study team and the participant, how long they will last, and where/how they will take place.

For the assessments there will be a screening visit at the time of enrollment, visit at baseline (either at the same time if the woman is ready to enrol or within 2 weeks afterwards if she would like more time to think about it), in late pregnancy, at delivery, and at 6 weeks postpartum. See above for assessments that will be done at each visit. We expect baseline and the 6 week postpartum visits to last between 1 to 1.5 hours. We expect the 3rd trimester visit to be shorter, around 45 minutes. We expect the birth visit to only entail 5 minutes of data collection with the women, while the rest will be gathered from medical records.

For women randomized to the intervention, there will be 6 core intervention sessions and up to 2-6 booster sessions (depending on the time of enrolment). The first five core sessions will be delivered weekly as early in the pregnancy as possible, then the booster sessions will occur, with one final core session (Core Session 6) in the 3rd trimester. Booster sessions will be scheduled on a case by case basis, depending on the recruitment time of the pregnant mother. Please see Table 2 above for an outline of session content.

For women in the biological substudy, there will be an additional visit at 24 weeks gestation for a blood draw and HADS administration. See the Figure below for a timeline of study visits.

Figure: Timeline for participants in the intervention and control arms of the main trial

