The proposed study is a single-blind, individual randomized clinical trial. The assessment team, trial statistician, and PIs will be masked to allocation status of study participants. To maintain masking during the trial, intervention and assessment teams will not have any interaction during the trial, as they will be placed at separate locations within the Obstetrics Department of HFH. Furthermore, participants will be instructed not to disclose which type of treatment they are receiving to the assessment team. Fidelity of masking will be measured by having assessors guess the trial arm of each participant at the end of follow-up assessment. We hypothesize that assessors will only be able to correctly guess the condition of participants at a chance rate of nearly 50% at follow-up assessments, indicating that masking is maintained.

2. Will participants receive standard care or have current therapy stopped?

Each woman randomized into the HMHB intervention arm will receive the HMHB intervention program plus usual care. Women allocated to the control condition will get usual care (slightly enhanced) alone. The WHO recommends eight antenatal visits for positive pregnancy experience (43) which we will be the target number of visits for study participants in the control group (depending on their gestational week). These visits will involve evaluating health status, discussing any concerns, and performing routine exams consistent with stage of pregnancy. Usual care will also be enhanced by medical staff at the hospital receiving additional training in mental health treatment to counsel participants. Transportation will also be provided or facilitated for participants to assist with attending appointments and the study will pay for any ultrasounds needed.

3. Will you use a placebo or non-treatment group, and is that justifiable?

The control arm will receive a slightly enhanced version of usual care, which we consider is justifiable.

4. Explain when you may remove a participant from the study.

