Missed sessions or early withdrawal (i.e., withdrawal before all sessions are completed) from the HMHB intervention or from the schedule of visits for the control group, will not result in investigator/research team-initiated withdrawal from the study; in such cases of missed visits, remaining study procedures can and should be completed as indicated by the study protocol. If a clinically significant finding is identified (including but not limited to changes from baseline) after enrollment, the HBHM trainer, assessor or hospital staff will refer the case to Co-I [name] (a psychologist and the main intervention supervisor) and Co-I [name] (a psychiatrist and the main field supervisor) to determine if any change in participant management is needed. Any new clinically relevant finding will be reported as an adverse event (AE).

Participants are free to withdraw from the study at any time upon request. An investigator may discontinue or withdraw a participant from the study for the following reasons:

- Death of participant.
- Women who develop suicidal ideation who are unable to participate because of their care
- Participant moves from the study area.
- Acute, chronic, or long-term physical or psychiatric illness in the participant leading to inpatient hospitalization during the study
- Any clinical AE, laboratory abnormality, or other medical condition or situation occurs such that continued participation in the study would not be in the best interest of the participant
- Disease progression that requires discontinuation of the intervention

The reason for participant termination or withdrawal from the study will be recorded. Women with a miscarriage, stillbirth or neonatal death before the 6 week postpartum visit will still be included in the study for the 6 week postpartum mental health outcomes, although they may not be able to provide data for other child-related outcomes.

A participant will be considered lost to follow-up if he or she fails to return to the endpoint assessment (i.e., 6 weeks postpartum) and/or is unable to be contacted by the study site staff.

The following actions will be taken if a participant fails to return to the clinic for a required study visit:

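### The PIs are declared masked, yet adverse events found by HMHB providers go first to a site PI, which discloses those women's arm

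*Combined protocol and SAP*

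**What the plan says.** Section V, at the question on whether study staff are blind to intervention status, gives the list of masked parties: "The assessment team, trial statistician, and PIs will be masked to allocation status of study participants". It makes no exception for any PI.

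Section X.D describes two entry points for adverse events. Events found by assessors are entered on tablets, and the data manager reports them daily to a Co-I. The second entry point is different: "AEs detected by the non-specialist providers will be first reported to [name] (one of the site PIs) who will complete the AE report". After either, the data manager passes the event to an independent psychiatrist or physician, who writes a narrative. The data manager removes identifying information from that narrative before it reaches a site PI and then the PI.

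On who the providers see, the randomization paragraph under Study Implementation in Section V says: "Each woman randomized into the HMHB group will be assigned to a HMHB non-specialist provider". The same section has them deliver the HMHB sessions. Control women receive usual care from hospital medical staff.

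On removal from the study, Section V says "An investigator may discontinue or withdraw a participant from the study for the following reasons" and includes among those reasons a clinical adverse event that makes staying in contrary to the woman's best interest.

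**The concern.** The two statements cannot both be followed. If a provider tells a site PI about an adverse event, the source of the report identifies the arm. The final report could then not truthfully say that the PIs were masked, although the protocol presents this as a feature of the design.

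The people concerned are not peripheral. Section X.A says "The PI and Site Co-PIs will be primarily responsible for monitoring the trial", and Section X.B says of recording and storing study data that two investigators, "as the local-PIs, will be monitoring this regularly". Someone who oversees conduct and records would know the allocation of some women, all of them in one arm. In principle that knowledge could colour how an event is handled, or whether a woman is kept in the study.

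**Working it through.** The point rests on reading four places together. The plan gives no figure to reproduce.

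1. **Does the word PIs include site PIs?** Section X.A names one study PI plus Site Co-PIs, Section X.B speaks of local PIs, and Section X.D of site PIs. The plural in the masking statement has no other natural reading.

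2. **Does a provider's report reveal the arm?** Providers deliver HMHB and are assigned to women randomized to HMHB. Control women have no such provider. So P(woman is in HMHB | report comes from a provider) = 1 by design.

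3. **Does the later de-identification cure this?** No, for two reasons. The site PI has already taken the first report and completed the form before the narrative exists. And the step described removes identity; it does not mention removing the arm, while the narrative is required to discuss the event's relationship to the intervention.

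4. **Is there an exemption elsewhere?** None was found. No section excludes a site PI from the masking statement or names an unmasked recipient for provider-detected events.

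5. **How many women?** Planned enrollment is 1,200, 600 per arm. The number whose arm is disclosed by this route lies between 0 and 600, so at most 600/1,200 = 50% of the trial, and only in HMHB. Each HMHB woman has 6 + 2 = 8 to 6 + 6 = 12 planned provider sessions, so the route is open throughout the intervention, but sessions are opportunities and not events. The documents give no adverse event rate, so the count cannot be narrowed.

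6. **Does it reach the primary outcome?** The primary endpoint is a SCID diagnosis at six weeks postpartum. It is made by assessors who are masked, are placed apart from the intervention team, and are not on the provider reporting route.

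**The case against.** The strongest reply is that the masking that matters is intact. The design overview in Section III ties the term single-blind to the masked assessment team, and nothing here breaches that. It is also reasonable for a senior clinician to hear first about events found by providers, who have no prior experience in mental healthcare delivery. Both points stand. They limit the importance of the conflict; they do not remove it, because the protocol separately lists the PIs as masked.

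A reader might go further and infer that arm-aware withdrawal would make six-week outcomes missing differently by arm. The documents do not support that as more than a possibility. The withdrawal text speaks only of an investigator and does not say which one decides. Clinically significant findings already go elsewhere: "the HBHM trainer, assessor or hospital staff will refer the case to Co-I [name] (a psychologist and the main intervention supervisor", with a psychiatrist Co-I, to decide on management. Co-Is are not on the masked list, and an intervention supervisor would know the arm by role, so some arm-aware judgement exists whatever happens to the adverse event form. Withdrawal is also tied to the woman's best interest, and missed sessions are not grounds for it.

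A reader might also infer that control women's events have no route to the investigators. That is wrong: assessors and hospital staff see both arms and refer cases from both. Only the provider channel is confined to HMHB.

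Finally, the Table 4 footnote on the intimate partner violence screener, whose purpose is to "refer women with IPV to counseling, since it is considered an adverse event", might suggest heavy traffic on the provider route. It does not. The screener is a scheduled assessment item, so a positive answer enters by the assessor route.

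**Conclusion.** The inconsistency is real and minor. As written, a site PI learns the arm of every woman with a provider-reported adverse event, so the statement that the PIs are masked does not describe this design. This rests on two readings: that the plural includes site PIs, and that providers see only HMHB women. The text supports both.

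The number of women affected is unknown, between 0 and 600. Bias in the SCID ratings is not claimed, since the assessors stay masked. Arm-aware handling or withdrawal after an adverse event is a possible risk only, and no effect on the primary comparison is shown. Because names are redacted, it cannot be told whether the site PI who receives these reports also takes part in withdrawal decisions.

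**What to change.** **Preferred.** In the second bullet of Section X.D, have the HMHB supervisor, who knows the arm by role, complete the adverse event form on the tablet. It then goes to the data manager and on to the independent psychiatrist or physician already provided for. Site PIs receive the narrative with identity removed and, where possible, the arm as well. Keep an exception that lets a site PI be told at once of an urgent safety event, and log each use. Having the supervisor complete the form, and not the provider, keeps a senior first check.

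**Alternative.** If a site PI must remain the first recipient, amend the masking statement in Section V to say that this person is not masked for women with provider-reported events, and say so in the trial report.

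**In either case.** Take the independent clinician's advice before any withdrawal related to an adverse event. Tabulate by arm the withdrawal reasons that Section V already requires to be recorded.

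**Cost.** A few sentences in Sections V and X.D and, under the preferred option, a different person completing one form. No new visits or staff are needed. Under that option a site PI hears of non-urgent provider-detected events slightly later, and the urgent exception will still unmask a site PI for some women, which is why it should be logged.
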